14. Treatment with any antiviral drugs (except remdesivir or other authorized treatments for COVID-19), or with any drugs known to be strong inducers or inhibitors of cytochrome P450 isoform (CYP) 2C19, CYP3A4, CYP2C8, and CYP2E1 within 14 days or 5 half-lives prior to the start of study treatment. Drugs with a narrow therapeutic index that are substrates of 1A2, 2B6, 2C8, 2C9, 2C19, 3A, and 2D6 are also prohibited.

15. Inability to swallow oral medications or a gastrointestinal disorder with diarrhea (eg, Crohn's disease), malabsorption, or diarrhea of any etiology at baseline.

16. Any other clinically significant medical condition or laboratory abnormality that, in the opinion of the investigator, would jeopardize the safety of the patient or potentially impact patient compliance or the safety/efficacy observations in the study.

Test product, dose, and mode of administration:

Antroquinonol in a dose of 100 mg (1 capsule) administered BID orally, for 14 days.

Reference therapy, dose, and mode of administration:

Placebo (1 capsule) administered BID orally, for 14 days.

Duration of patient participation in study:

Total duration of patient participation is planned to be a maximum of 33 days.

The screening period is planned to be up to 3 days. The planned study treatment duration is 14 days.

Follow-up/EOS assessments will be performed on Day 28 (± 2 days).

Study populations:

Intention-to-treat (ITT): All randomized patients. Patients will be analyzed according to the treatment to which they were randomized.

modified ITT (mITT): All randomized patients who received at least 1 dose of study drug.

Per Protocol Set (PPS): All patients from the ITT set who have no important protocol deviations during the study. Patients with any important protocol deviations shall be excluded from the PPS prior to database lock.

Safety Set (SS): All patients who have received at least 1 dose of the study treatment. Patients will be analyzed according to the study treatment they actually received.

Pharmacokinetic Set (PKS): Patients in the sentinel cohort who have received at least 1 dose of the study treatment and have at least 1 evaluable plasma concentration without important protocol deviations or events thought to significantly affect the PK.

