7.2. Safety Assessments

7.2.1. Adverse events

7.2.1.1. *Definitions*

Adverse event definitions and assignment of severity and causality are detailed in [Appendix 1](#).

Adverse events will be elicited from the patient (or, when appropriate, from a caregiver, surrogate, or the patient's legally authorized representative) by the study site staff using a nonleading question such as "How are you feeling today?" or "Have you had any health concerns since your last visit?"

The investigator and any designees are responsible for detecting, documenting, and reporting events that meet the definition of an AE or SAE and remain responsible for following up AEs that are serious, considered related to the study treatment or the study, or that caused the patient to discontinue the study treatment.

Adverse events will be assessed from signing the ICF until 2 weeks after the last dose of study treatment (Day 28 ± 2 days) as noted in the Schedule of Assessments table ([Appendix 5](#)).

Adverse events will be coded according to the Medical Dictionary for Regulatory Activities (MedDRA) version 23.0 dated 19 April 2020 (exclusively meant for COVID-19) or later.

7.2.1.2. *Reporting serious adverse events*

Serious AE reporting will be carried out as per local/country regulations, and will be described in the Safety Management Plan.

All SAEs occurring after the signing of the ICF until 30 days following last dose of the study treatment and regardless of study treatment relationship, must be reported to Covance within 24 hours of obtaining knowledge of the event. The report should include all available information requested on the SAE form.

Serious AEs - Covance PSS

E-mail: [contact] (standard)

The SAE form will collect data surrounding the event (eg, the nature of the symptom[s], time of onset in relation to initiation of therapy, duration, intensity, and whether or not therapy was discontinued). The investigator's assessment of the probable cause of the event will also be included. In addition, relevant medical history, concomitant medications, laboratory and diagnostic tests reports, and procedures as well as all pertinent medical information related to the event will also be collected.

Covance PSS will forward SAE queries requesting incomplete or missing information directly to the investigator. It is the investigator's responsibility to be diligent in providing this information back to Covance PSS as soon as it is available.

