7.2.2. Pregnancy

Female patients of childbearing potential will take a pregnancy test during screening (or pretreatment on Day 1), discharge, ET/EOT, and at the Day 28 Follow-up/EOS visit. Additionally, local/country regulations will be followed as applicable (eg., a pregnancy test one month following the last dose of study treatment in female patients of childbearing potential).

A urine pregnancy test may be performed but must be confirmed with a serum pregnancy test (screening only). The Follow-up/EOS visit test will be a urine pregnancy test only (pregnancy test kit will be provided to the patient when discharged).

Following administration of study treatment, pregnancy cases in any patient who is a female of childbearing potential or female partner of a male patient will be reported if known until the patient completes or withdraws from the study. The pregnancy will be reported immediately by telephone and by faxing a completed pregnancy report to the sponsor (or designee) within 24 hours of knowledge of the event. The pregnancy will not be processed as an SAE; however, the investigator will follow the patient until completion of the pregnancy and must assess the outcome in the shortest possible time. Generally, the follow-up will be no longer than 6 to 8 weeks following the estimated delivery date.

The investigator should notify the sponsor (or designee) of the pregnancy outcome by submitting a follow-up pregnancy report. If the outcome of the pregnancy meets the criteria for immediate classification of an SAE (eg, spontaneous or therapeutic abortion [any congenital anomaly detected in an aborted fetus is to be documented], stillbirth, neonatal death, or congenital anomaly), the investigator will report the event by telephone and by faxing a completed SAE form to the sponsor (or designee) within 24 hours of knowledge of the event.

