The investigator will collect pregnancy information on any female patient who becomes pregnant while participating in this study. Information will be recorded on the appropriate form and submitted to the sponsor (or designee) within 24 hours of learning of a patient's pregnancy. The patient will be followed to determine the outcome of the pregnancy.

The investigator will attempt to collect pregnancy information on any male patient's female partner who becomes pregnant while the male patient is in this study. After obtaining the necessary signed informed consent from the pregnant female partner directly, the investigator will record pregnancy information on the appropriate form and submit it to the sponsor (or designee) within 24 hours of learning of the partner's pregnancy. The female partner will also be followed to determine the outcome of the pregnancy.

Information on the status of the mother and child will be forwarded to the sponsor (or designee). Generally, the follow-up will be no longer than 6 to 8 weeks following the estimated delivery date. Any termination of the pregnancy will be reported regardless of fetal status (presence or absence of anomalies) or indication for the procedure.

While pregnancy itself is not considered to be an AE or SAE, any pregnancy complication or elective termination of a pregnancy will be reported as an AE or SAE. A spontaneous abortion is always considered to be an SAE and will be reported as such. Any poststudy pregnancy-related SAE considered reasonably related to the IMP by the investigator will be reported to the sponsor. While the investigator is not obligated to actively seek this information in former study patients, he or she may learn of an SAE through spontaneous reporting.

Events not to be reported as adverse events

A lack of drug effect is not an AE in this study because the purpose of the clinical study is to establish treatment effect.

The following study-specific clinical events related to Coronavirus Disease 2019 (COVID-19) are exempt from AE reporting unless the investigator judges the event to be related to study drug:

- Hypoxemia due to COVID-19 requiring non-invasive ventilation or high flow oxygen;
- Respiratory failure due to COVID-19 requiring invasive mechanical ventilation or extracorporeal membrane oxygenation

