Appendix 4. Contraceptive Guidance

Definitions

Female Patients of Childbearing Potential: Premenopausal female study patients who are anatomically and physiologically capable of becoming pregnant following menarche.

Female Patients of Nonchildbearing Potential:

1. **Surgically sterile:** Female study patients who are permanently sterile via hysterectomy, bilateral salpingectomy, and/or bilateral oophorectomy by reported medical history and/or medical records. Surgical sterilization to have occurred a minimum of 6 weeks, or at the investigator's discretion, prior to screening.
2. **Postmenopausal:** Female study patients at least 45 years of age with amenorrhea for at least 24 months without an alternative medical reason.

Fertile male: A male that is considered fertile after puberty.

Infertile male: Permanently sterile male via bilateral orchiectomy.

Contraception Guidance

Female Patients

Female patients who are of nonchildbearing potential will not be required to use contraception. Female patients of childbearing potential must be confirmed as not being pregnant at screening or pretreatment on Day 1 and be willing to use an acceptable highly-effective method of birth control from the time of signing the informed consent form (ICF) until 90 days after the last dose of study treatment. Additionally, local/country regulations will be followed as applicable (eg., monthly pregnancy test after the last dose of study treatment in female subjects of childbearing potential). Acceptable methods of contraception include:

- hormonal injection (as prescribed)
- combined oral contraceptive pill or progestin/progestogen-only pill (as prescribed)
- combined hormonal patch (as prescribed)
- combined hormonal vaginal ring (as prescribed)
- surgical method performed at least 90 days prior to the screening visit:
 - bilateral tubal ligation
 - Essure® (hysteroscopic bilateral tubal occlusion) with confirmation of occlusion of the fallopian tubes
- hormonal implant

- hormonal or nonhormonal intrauterine device
- vasectomized male partner (sterilization performed at least 90 days prior to the screening visit) with verbal confirmation of surgical success, and the sole partner for the female patient.

Female patients of childbearing potential should refrain from donation of ova from the first dose through 90 days after the last dose of study treatment.

Male Patients

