Male patients (even with a history of vasectomy) with partners of childbearing potential must use a male barrier method of contraception (ie, male condom with spermicide) in addition to a second highly effective method of acceptable contraception from the first dose through 90 days after the last dose of study treatment. Acceptable methods of contraception for female partners include:

- hormonal injection
- combined oral contraceptive pill or progestin/progestogen-only pill
- combined hormonal patch
- combined hormonal vaginal ring
- surgical method (bilateral tubal ligation or Essure [hysteroscopic bilateral tubal occlusion])
- hormonal implant
- hormonal or nonhormonal intrauterine device.

An acceptable second method of contraception for male patients is vasectomy that has been performed at least 90 days prior to the screening visit, with verbal confirmation of surgical success.

For male patients (even with a history of vasectomy), sexual intercourse with female partners who are pregnant or breastfeeding should be avoided unless condoms are used from the first dose until 90 days after the last dose of study treatment. Male patients are required to refrain from donation of sperm from the first dose through 90 days after the last dose of study treatment.

Sexual Abstinence and Same-sex Relationships

Patients who practice true abstinence, because of the patient's lifestyle choice (ie, the patient should not become abstinent just for the purpose of study participation), are exempt from contraceptive requirements. Periodic abstinence (eg, calendar, ovulation, symptothermal, postovulation methods) and withdrawal are not acceptable methods of contraception. If a patient who is abstinent at the time of signing the ICF becomes sexually active, he or she must agree to use contraception as described previously.

For patients who are exclusively in same-sex relationships, contraceptive requirements do not apply. If a patient who is in a same-sex relationship at the time of signing the ICF becomes engaged in a heterosexual relationship, he or she must agree to use contraception as described previously.

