- b Initial sentinel cohort of 20 patients to be enrolled to assess safety, tolerability, efficacy, and PK. Enrollment will pause after the 20th patient in the sentinel cohort has started treatment, until the results of the interim analysis are known. Once the 20th patient in the sentinel cohort has completed 14 days of treatment, an unblinded DMC will assess the safety, tolerability, efficacy, and PK of 100 mg BID antroquinonol in COVID-19 patients in the sentinel cohort (interim analysis 1). The DMC will issue a recommendation to enroll patients for the expansion cohort, or to stop the study depending on the safety and futility assessment. Once the 80th patient has been enrolled and completed 14 days of treatment, the DMC will review the safety, tolerability and efficacy data (interim analysis 2). Enrollment may be restricted at the 100th patient until the DMC has completed the assessment to prevent excessive enrollment.
- c Patients must satisfy all of the criteria at the screening visit unless otherwise stated (e.g. some criteria can be evaluated at Day 1 if needed).
- d Daily study treatment administration from Day 1 to Day 14.
- e A complete physical examination (general appearance, HEENT, lymphatic, cardiovascular, respiratory, gastrointestinal, musculoskeletal, neurological, and dermatological systems) will be performed at screening. Vital signs (respiratory rate, temperature, blood pressure, and pulse rate) to be assessed during hospitalization, on discharge, ET/EOT and Follow-up/EOS visit (for site or in-person visits only). Pulse oximetry to measure SpO₂ will be collected in the eCRF at screening (room air) after screening with vital

signs (Day 1; Day 3, Day 5, Day 7, Day 14/EOT and/or Discharge/ET visits, Day 28 if patient is in hospital). FiO₂ data will be collected the same days as vital signs. PaO₂ will be collected if done as part of the standard of care. Height and body weight will be measured only at screening. After patient is discharged from hospital, SpO₂ should be collected at Day 5 and Day 14 if visits completed in clinic/hospital. Values collected by a home health provider may be utilized, but are not required (refer to [Section 7.2.4.2](#)). Body temperature will be measured according to site's local practices and may include oral, tympanic, rectal, axillary, or frontal.

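### Pregnancy reporting closes at about Day 28, although contraception and donation limits run to about Day 104, and the protocol's two reporting rules disagree

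*Protocol*

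**What the plan says.** **Reporting.** Protocol Section 7.2.2 covers pregnancies after study treatment has been given, in female patients of childbearing potential and in female partners of male patients. They "will be reported if known until the patient completes or withdraws from the study". A reported pregnancy is followed to its outcome, generally no later than 6 to 8 weeks after the estimated delivery date. Appendix 1 (Pregnancy) uses a different test: it collects pregnancies that start during the patient's participation, including any "female partner who becomes pregnant while the male patient is in this study". Under both sections the site has 24 hours from learning of the pregnancy to report it.

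**Study end.** Appendix 5, footnote d, specifies "Daily study treatment administration from Day 1 to Day 14". The synopsis puts the follow-up/end-of-study (EOS) assessment at Day 28, with a window of 2 days either side.

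**Precautions.** Appendix 4 asks female patients of childbearing potential to use "birth control from the time of signing the informed consent form (ICF) until 90 days after the last dose of study treatment". Men with partners of childbearing potential must use contraception "from the first dose through 90 days after the last dose of study treatment", and a vasectomy does not exempt them from the barrier method. Section 4.1, inclusion criterion 10, makes the 90-day limits on sperm and ova donation a condition of entry.

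**After the study.** Section 7.2.1.2 requires every SAE up to 30 days after the last dose to be reported, whatever its cause. Appendix 1 always counts a spontaneous abortion as an SAE. It also makes later pregnancy-related SAEs reportable if the investigator judges them related to the product, but the investigator need not look for them. Sections 7.2.2 and 7.2.3, Appendix 4 and Appendix 5 (footnote g) allow further pregnancy tests where local rules ask for them.

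**The concern.** The protocol asks both sexes to avoid conception and donation for 90 days after the last dose, but it stops asking about new pregnancies roughly two weeks after that dose. Outcome follow-up starts only once a pregnancy is reported, so a pregnancy that need not be reported is not followed.

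What is at stake is safety information. Section 1.2 gives cumulative exposure to antroquinonol as 161 subjects, so any pregnancy in a treated patient or partner would be informative and hard to recover later. Partners of male patients have no scheduled pregnancy test, so their pregnancies come to light only if someone tells the site.

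The present rules also capture outcomes unevenly. A spontaneous abortion on Day 40 would be reportable as an SAE. A continuing pregnancy that began on the same day as that one, and was first learned of on Day 40, would fall outside Section 7.2.2.

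**Working it through.** **Inputs.** Last planned dose: Day 14 (Appendix 5, footnote d). End of study: Day 28, allowed range Day 26 to Day 30 (synopsis, Appendix 5). Precautions: 90 days after the last dose (Section 4.1, Appendix 4). SAE reporting: 30 days after the last dose (Section 7.2.1.2).

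**The plan's own figure.** Section 7.2.1.1 equates Day 28 with two weeks after the last dose. Check: 28 − 14 = 14 days. It reproduces. The documents give no figure for the share of the 90 days that is covered.

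**End of the precaution period.** 14 + 90 = Day 104.

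**Uncovered share** = (90 − (EOS day − last-dose day)) / 90.

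| Case | Days covered | Days not covered | Share not covered |
|---|---|---|---|
| Last dose Day 14, EOS Day 28 | 14 | 76 | 84.4% |
| Last dose Day 14, EOS Day 26 | 12 | 78 | 86.7% |
| Last dose Day 14, EOS Day 30 | 16 | 74 | 82.2% |
| Last dose Day 10, followed to Day 28 | 18 | 72 | 80.0% |
| Last dose Day 1, followed to Day 28 | 27 | 63 | 70.0% |
| Withdraws from the study on the last dosing day | 0 | 90 | 100% |

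The denominator is the 90 days after the last dose. Counted from the first dose (Days 1 to 104), the uncovered part is 76/104 = 73.1%.

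**SAE route.** 14 + 30 = Day 44. This leaves 60 of the 90 days (66.7%) beyond the general SAE window. Within that window it captures only events that qualify as SAEs, not an uncomplicated pregnancy.

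**The two rules side by side, for a completer with EOS on Day 28.**

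| Pregnancy | Section 7.2.2 | Appendix 1 |
|---|---|---|
| Begins Day 10, known before Day 28 | Reported | Reported |
| Begins Day 10, learned of on Day 40 | Outside (not known in time) | Arguably inside (began in the study; no limit on when the site learns) |
| Begins on any of Days 29 to 104 | Outside | Outside, unless a pregnancy-related SAE judged related to the product |

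Locally required tests after Day 28 do not close the gap. They depend on the country, they apply only to female patients, and a positive result would arrive after Section 7.2.2 has closed.

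**The case against.** The strongest reply is that the period of greatest interest is already covered. Pregnancies from the first dose to Day 28 are reportable. Female patients of childbearing potential are tested at screening or Day 1, at discharge, at end of treatment or early termination, and at Day 28. A reported pregnancy is followed well past study end. This stands. A reader might infer that the trial would report no exposed pregnancies; the documents do not support that. It would miss those that begin later and, under Section 7.2.2, those recognised later.

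Second, the protocol never calls the 90 days a risk period. That is an inference from contraception and donation rules. The longest mean half-life in Section 1.2.3 is 7.643 hours, from a different population and dose, so Day 28 is 336/7.643, or about 44 half-lives, after a Day 14 dose. For female patients, conceptions after Day 28 would then involve little circulating parent drug. This is a fair caution against treating all 90 days as equally important. It does not explain why the precautions and the reporting end on different days, and it does not address partners of male patients.

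Third, it is tempting to say that both sections exclude a pregnancy conceived on treatment and recognised after Day 28. Only Section 7.2.2 does so; Appendix 1 arguably includes it. What stands is a conflict between the two, not a double exclusion.

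Fourth, withdrawal with none of the 90 days covered is an extreme case. Section 4.4.3 asks patients who stop treatment to continue assessments to Day 28, and Section 4.4.7 asks those who withdraw to complete the final visit.

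Finally, the consent form and the Safety Management Plan are not among the documents reviewed. An instruction to report later pregnancies could be there; this cannot be checked.

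**Conclusion.** The mismatch holds as an internal inconsistency in safety data collection. For a patient dosed to Day 14, pregnancies that begin in 76 of the 90 days covered by the precautions (84%; 82% to 87% over the EOS window) need not be reported or followed, apart from the SAE routes. Separately, Section 7.2.2 and Appendix 1 give a site different answers for a pregnancy that begins in the study and is learned of afterwards.

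The percentage is a share of calendar days. It assumes a last dose on Day 14 and follow-up to the scheduled end of study; with earlier stopping but follow-up to Day 28, the share is 70% (last dose Day 1) to 80% (last dose Day 10). It does not estimate how many pregnancies would be missed, and the documents give no basis for one. Nor does it show that later pregnancies carry drug-related risk. No efficacy or statistical conclusion of the trial depends on this point. It is a modest gap, worth closing because the correction is cheap.

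**What to change.** Replace the two reporting rules in Section 7.2.2 and Appendix 1 with one, matched to the 90 days that the protocol already uses:

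> Pregnancies in female patients, and in female partners of male patients, that begin from the first dose through 90 days after the last dose are reported within 24 hours of the site learning of them, whenever that is, and followed to outcome. This includes pregnancies learned of after study completion, treatment discontinuation or study withdrawal, subject to consent.

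At the existing Day 28 contact, ask each patient to tell the site of any such pregnancy. State the same in the consent form, and align the Safety Management Plan if it addresses pregnancy.

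The change leaves dosing, contraception rules, visits and tests as they are.

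**Cost.** Protocol and consent wording; a passive reporting line open for about 11 more weeks (76 days / 7 = 10.9); and, for each additional pregnancy reported, follow-up to outcome and, for partners, the separate consent that Appendix 1 already requires. Capture would still depend on patients contacting the site.
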